F. Sample Size Estimation and Accrual

The endpoint of this pilot trial will be an immunological endpoint, i.e., the immune response rate at 6 months. Based on published results from a randomized trial using sipuleucel-T only in this population, in which proliferative T-cell responses specific for PAP were detected in 15 of 55 (27.3%) patients after immunization [7], and results from a phase I trial with this DNA vaccine only in which PAP-specific cytolytic T-cell responses were amplified after immunization in 7 out of 12 (58%) evaluable patients [23], it is anticipated that the immune response rate in the sipuleucel-T alone arm (Arm 1) will be 25% and that the addition of the pTVG-HP vaccine (Arm 2) will boost the response rate to at least 75%. An increase of 50% in the immune response rate will be considered as a clinically important difference. The following table shows the required sample sizes (per arm) to detect various differences in the immune response rates between the two arms with 80% power at the one-sided 5% significance level. These calculations are based on the stratified Mantel-Haenszel test with exact p-values.

Table 12.1 *Required sample sizes (per arm) to detect various differences in the immune response rates between the two arms with 80% power at the two-sided 5% significance level*

Immune Response Rate Arm 1 (sipuleucel-T alone arm)	Immune Response Rate: Arm 2 (sipuleucel-T + pTVG-HP vaccine arm)			
	70%	75%	80%	85%
15%	12	10	9	9
20%	15	12	10	9
25%	18	14	12	10
30%	23	18	15	12

A sample size of 14 patients per arm is proposed for this trial. This sample size is sufficient to detect an anticipated difference in the immune response rate of at least 50% (i.e., $\geq 75\%$ in Arm 2 vs. 25% in Arm 1) with adequate power ($\geq 80\%$) at the one-sided 5% significance level. The following table shows the attainable power levels to detect various differences in the immune response rates between arms at the one-sided 5% significance level, assuming a sample size of 28 evaluable (for immune response) patients.

Table 12.2: *Attainable power levels to detect various differences in the immune response rates between the two arms at the one-sided 5% significance level, assuming a sample size of 14 evaluable patients per arm*

	Immune Response Rate: Arm 2 (sipuleucel-T + pTVG-HP vaccine arm)			
Immune Response Rate Arm 1 (sipuleucel-T alone arm)	70%	75%	80%	85%
15%	85%	91%	96%	98%
20%	76%	85%	91%	96%
25%	65%	80%	84%	91%
30%	53%	65%	76%	85%

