A difference in the immune response rate of 55% between the two arms will be detected with at least 84% power. Analogously, a difference in the efficacy response rate of only 40% between the two arms will be detected with 53% power at the one-sided 5% significance level. In order to account for unevaluable patients, 30 eligible patients (15 per arm) will be accrued and randomized. Based on past experience with this patient population treated at our institution, we anticipate that the proposed total number of 30 patients will be accrued within 18 months. Each patient will be followed for at least 12 months.

G. Statistical Analysis Plan

G.1. General

This section outlines the statistical analysis strategy and procedures for the study. If after the study has begun changes are made to primary and/or key secondary objectives, or the statistical methods related to those objectives, then the protocol will be amended.

Summary tabulations will be presented that will display the number of observations, mean, standard deviation, median, range, minimum, and maximum for continuous variables and the number and percent per category for ordinal and categorical data. All endpoints of this study will be presented graphically where possible using boxplots and histograms for continuous variables and (stacked) bar charts for categorical variables. Data analysis will be performed using SAS[®] (SAS Institute Inc., Cary, North Carolina) version 9.2 or greater.

There are many comparisons made between the two trial arms for multiple measurements, both clinical and laboratory. However, since this a pilot study, no adjustment will be made for

multiple comparisons. Except for the primary immunological endpoint, where the comparison between arms will be conducted at the one-sided 0.05 significance level, all other comparisons will be made using a two-sided test at a significance level of 0.05 without adjustment for multiplicity.

G.2. Baseline Comparability

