All measurements (variables) collected at baseline will be summarized and compared between study arms. These include demographic variables, lab parameters (CBC and platelets, creatinine, alk phos, SGOT, total bilirubin, amylase, LDH, serum testosterone and PSA and PAP) and medical history information. Comparisons between study arms of baseline variables on a continuous scale will be performed using a two-sample t-test and/or nonparametric Wilcoxon Rank Sum test. Comparisons between study arms of baseline variables on a categorical scale will be performed using Fisher's exact test.

G.3. Analysis of the Primary Immunological Endpoint: Immune Response Rate

Immune responses, obtained at 6 months, will be summarized in tabular format. Ninety-five percent confidence intervals for the proportions of patients with an immune response will be constructed for each study arm. The comparison of immune response rates between study arms will be performed using the Cochran-Mantel-Haenszel test, stratified by estimated survival (< 18 months, \geq 18 months) using the Halabi nomogram [50]. Due to the small sample size, exact p-values will be computed using Zelen's exact test for equal odds ratios for stratified 2 X 2 tables.

As a secondary analysis, "durable" immune responses will be determined by the presence of immune responses at one or more of the 3, 9, and 12 month time points evaluated after randomization. Immune responses determined at the 3, 9 and 12 month time points will be summarized in tabular format and compared between study arms using the Cochran-Mantel-Haenszel test, stratified by estimated survival (< 18 months, \geq 18 months) using the Halabi nomogram [50]. Furthermore, a generalized linear mixed effects model for binomial data with a logit link function will be employed to evaluate the longitudinal effects of immune responses measured at the 3-month intervals.

G.4. Analysis of Secondary and Exploratory Clinical and Immunological Endpoints

G.4.1. Analysis of 12-month Progression-Free Survival Rate

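### The Table 12.1 caption says two-sided 5%, but its sample sizes are one-sided, and the 25% vs 75% cell needs correcting in the same edit

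*Combined protocol and SAP*

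**What the plan says.** Section 12.F labels Table 12.1 in two ways. The sentence that introduces it offers sizes "to detect various differences in the immune response rates between the two arms with 80% power at the one-sided 5% significance level". The caption gives the same sizes "with 80% power at the two-sided 5% significance level".

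The other statements about the primary comparison are one-sided. After the table, Section 12.F justifies 14 patients per arm, for 25% against 75%, at a one-sided 5% level. Table 12.2 gives power "at the one-sided 5% significance level, assuming a sample size of 14 evaluable patients per arm". Section 12.G.1 sets the analysis: "Except for the primary immunological endpoint, where the comparison between arms will be conducted at the one-sided 0.05 significance level", and makes all other comparisons two-sided at 0.05.

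The method is stated as well. Section 12.F says: "These calculations are based on the stratified Mantel-Haenszel test with exact p-values". Section 12.G.3 plans a matching analysis: "Due to the small sample size, exact p-values will be computed using Zelen's exact test".

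**The concern.** A table of sample sizes can be checked only if its alpha, sidedness and power are stated correctly, and this is the table from which 14 per arm is read. Its caption and its introducing sentence cannot both be right. A reader who takes the caption at its word would credit 14 per arm with 80% power in a two-sided test at the design alternative. Because Section 12.G.1 makes the primary comparison the only one-sided test in the plan, its sidedness should read the same wherever it appears.

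**Working it through.** **Inputs.** From Section 12.F: Arm 1 rates of 15, 20, 25 and 30%; Arm 2 rates of 70, 75, 80 and 85%; the printed sizes; target power 80%; alpha 5%; exact p-values. Allocation is 1:1 (Section 12.E). Stratum sizes and stratum-specific rates are not given. The main check is therefore the unstratified Fisher exact test, as a simplification, followed by a stratified check.

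**Formula.** With n per arm, x responders in Arm 1 and y in Arm 2, power is the sum of Bin(x; n, p1) × Bin(y; n, p2) over all (x, y) with Fisher p ≤ 0.05. The one-sided p is the upper hypergeometric tail for y given x + y. The two-sided p sums all outcomes no more probable than the one observed.

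**Step 1: reproduce the printed sizes.** Smallest n per arm with at least 80% power:

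| Arm 1 | Printed (70/75/80/85%) | One-sided exact | Two-sided exact |
|---|---|---|---|
| 15% | 12, 10, 9, 9 | 12, 10, 9, 9 | 16, 12, 11, 9 |
| 20% | 15, 12, 10, 9 | 15, 12, 10, 9 | 18, 16, 12, 11 |
| 25% | 18, 14, 12, 10 | 18, **15**, 12, 10 | 23, 18, 16, 12 |
| 30% | 23, 18, 15, 12 | 23, 18, 15, 12 | 29, 23, 18, 16 |

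One-sided sizes match the printed ones in 15 of 16 cells, the exception being 25% vs 75%. Two-sided sizes match only at 15% vs 85%.

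**Step 2: power at the printed sizes, in percent.**

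| Arm 1 | One-sided (70/75/80/85%) | Two-sided (70/75/80/85%) |
|---|---|---|
| 15% | 85.3, 80.9, 81.0, 88.2 | 72.2, 64.2, 72.7, 81.2 |
| 20% | 80.7, 84.8, 80.5, 81.0 | 68.0, 71.6, 63.5, 72.7 |
| 25% | 83.5, **75.2**, 84.8, 80.9 | 73.1, **63.1**, 71.6, 64.2 |
| 30% | 80.9, 83.5, 80.7, 85.3 | 71.3, 73.1, 68.0, 72.2 |

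Two-sided power is 63.1% to 73.1% in 15 cells and 81.2% in one. One-sided power is 80.5% to 88.2% in 15 cells and 75.2% at 25% vs 75%.

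**Step 3: stratified check.** An exact conditional test with two strata, split as evenly as possible and with equal rates in both, gives two-sided power of 63.9% to 76.3%, with no cell at 80%. One-sided power is 79.9% to 88.4% in every cell except 25% vs 75% (75.4%). The two cells at 79.9% (20% vs 75% and 25% vs 80%, both n = 12) are 80% to rounding.

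**Step 4: the 25% vs 75% cell, one-sided.** Unstratified power is 75.2% at 14 per arm and 80.4% at 15. With two strata, 14 per arm gives 75.4% to 76.3% over splits from 7/7 to 13/1.

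**Step 5: cross-check on Table 12.2.** One-sided exact power at 14 per arm agrees with the printed values within 1 point in 15 of 16 cells. The exception is again 25% vs 75%, printed as 80% against 75.2%.

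**The case against.** The strongest objection is that the documents already settle the matter. The one-sided level is stated before Table 12.1, after it and in Table 12.2, and Section 12.G.1 fixes it for the analysis. One word in one caption is the outlier, and correcting it changes no test and no alpha. This stands, and it limits the point to a labelling error.

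A reader might go further and infer that the trial is under-sized for its primary test, since two-sided power at 25% vs 75% is about 63% with 14 per arm and 18 per arm would be needed for 80%. The documents do not support that. Those figures describe a two-sided primary test, which Section 12.G.1 rules out. They show only that the caption is wrong.

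A second objection is that the result depends on the method. An uncorrected two-sided pooled normal formula gives sizes within 2 of every printed cell, and an uncorrected two-sided z-test has at least 80% power at the printed sizes in 15 of 16 cells. But the plan names exact p-values, for both the sizing and the analysis. The normal formula also fits less well. It matches 9 of 16 printed sizes, against 15 for the one-sided exact test, and at 30% vs 70% it gives 56.8% where Table 12.2 prints 53%. The enumerated z-test comes closer to Table 12.2, mostly within about 2 points, but that table is itself captioned one-sided. What stands is that the caption is false under the plan's stated kind of test, not under every conceivable test.

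Finally, the main check drops the stratification. The stratified check leads to the same conclusion, although 15% vs 85% then falls below 80% two-sided as well.

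**Conclusion.** The Table 12.1 caption contradicts the rest of the plan, and under an exact test it is the caption that is wrong. The printed sizes are one-sided. Two-sided power at those sizes is about 63% to 73% in 15 of 16 cells (unstratified), or about 64% to 76% in all 16 with two near-equal strata. The contradiction itself needs no calculation; the figures show which label to keep. They assume equal response rates across strata, and stratum sizes that the documents do not give.

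This is a mislabel. It does not alter the decision threshold of the primary test or the planned enrolment, and it should not be read as a failure of error control. Changing the one word is not quite enough, however. At 25% vs 75% the printed 14 gives about 75% one-sided power, so a one-sided caption would still be untrue for the design cell unless that cell is dealt with too.

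**What to change.** In the caption of Table 12.1, replace two-sided with one-sided. In the same edit, either change the 25% vs 75% entry from 14 to 15, or keep 14 with a footnote that it gives about 75% one-sided power and that 15 per arm gives about 80%. Align the sentence claiming at least 80% power for 14 per arm, and the 80% entry in Table 12.2, with whichever is chosen, since both describe the same case.

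The cost is one word and one table entry or footnote, with the matching wording. The primary test, its one-sided 5% level and the planned enrolment of 30 stay as they are. A sentence giving two-sided power is optional and not needed, because no two-sided primary test is planned.

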C.2.4. PSA Response

PSA complete response will be defined a decrease in PSA to <0.2 ng/mL. The decrease must be confirmed with PSA measurement a minimum of four weeks later (confirmed PSA CR). PSA partial response will be defined as reduction of at least 50% in baseline PSA.

C.2.5. PSA Doubling Time

PSA doubling time (PSADT) will be defined as the time it takes for the PSA value to double. PSADT will be calculated for each patient pre-treatment and post-treatment. The pre-treatment PSADT will be calculated from all available values obtained within 3-6 months prior to study enrollment, up to and including the baseline value. The post-treatment PSADT will be calculated from all PSA values obtained beginning with the PSA value at day 1 and continuing until the end-of study value. The pre-treatment and post-treatment PSADT will be calculated for each patient as the log 2 divided by the slope of the log PSA line, based on the linear regression model of log (PSA value) on time.

C.2.6. Evaluable for Immune Response

All patients who complete sipuleucel-T treatment at weeks 0, 2, and 4, and who have an immune response assessment at month 6 will be evaluable for immune response.

C.2.7. Analysis Populations

The ITT population consists of all patients who are randomized. The per-protocol population is defined as all patients who have been treated according to protocol, i.e., all inclusion/exclusion criteria are satisfied, and adequate treatment compliance of sipuleucel-T treatment and vaccine (pTVG-HP) is achieved.

D. Study Design

The study is designed as a randomized, two-arm, open-label, single institution pilot trial. Study arms will be defined as follows:

Arm 1: sipuleucel-T – administered intravenously (i.v.) per standard of care biweekly, weeks 0, 2, and 4.

Arm 2: sipuleucel-T – administered intravenously (i.v.) per standard of care biweekly, weeks 0, 2, and 4
 pTVG-HP (100 µg) with rhGM-CSF (208 µg) administered intradermally (i.d.) biweekly 4 times, then every 3 months to complete a 1-year treatment period (i.e. weeks 6, 8, 10, 12, then months 6, 9)

Eligible subjects will be randomly assigned in 1:1 fashion to either Arm 1 or Arm 2.

E. Randomization and Stratification

Eligible patients will be randomized to the two study arms with an allocation ratio of 1:1. The randomization will be based on permuted blocks of size 2-4, stratified by estimated survival (< 18 months, ≥ 18 months) using the Halabi nomogram [50].

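### Section 12.F claims at least 80% power for 25% vs 75% with 14 evaluable patients per arm; the exact one-sided power is about 75%, and 15 per arm are needed for 80%.

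*Combined protocol and SAP*

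**What the plan says.** Section 12.F makes the 6-month immune response rate the basis of the sample size. For the control arm it expects that "the immune response rate in the sipuleucel-T alone arm (Arm 1) will be 25"%. For Arm 2 it expects 75% or more. On the size of effect that matters it says: "An increase of 50% in the immune response rate will be considered as a clinically important difference".

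On the method it says: "These calculations are based on the stratified Mantel-Haenszel test with exact p-values". The text sets 80% power at a one-sided 5% level, and section 12.G.1 uses the same one-sided level for the primary comparison. The caption of Table 12.1 instead reads "immune response rates between the two arms with 80% power at the two-sided 5% significance level".

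For 25% vs 75%, Table 12.1 prints 14 per arm and Table 12.2 prints 80% power at 14 evaluable per arm. Of the 14 per arm, the text says: "This sample size is sufficient to detect an anticipated difference in the immune response rate of at least 50"%, with at least 80% power.

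On losses it says: "In order to account for unevaluable patients, 30 eligible patients (15 per arm) will be accrued and randomized". Section 12.E says: "The randomization will be based on permuted blocks of size 2-4, stratified by estimated survival". It gives no stratum sizes and no response rates by stratum.

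**The concern.** The neighbouring cells raise the doubt before any calculation. The pairs 20/70 and 30/80 have the same 50-point gap as 25/75. Their summed binomial variance is slightly smaller: 0.20×0.80 + 0.70×0.30 = 0.370, against 0.25×0.75 + 0.75×0.25 = 0.375. Yet they are printed with 76% power and 15 per arm, while 25/75 is printed with 80% and 14.

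The 25% row of Table 12.2 (65, 80, 84, 91) climbs by 15, 4 and 7 points. The 20% row climbs by 9, 6 and 5, and the 30% row by 12, 11 and 9. With 75 in the design cell, the 25% row would climb by 10, 9 and 7.

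This cell is the stated justification for the sample size of the primary endpoint. If it is wrong, the plan overstates its power, and the fifteenth patient per arm, described as cover for unevaluable patients, is needed just to reach 80%.

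**Working it through.** **Inputs.** From section 12.F: p1 = 0.25, p2 = 0.75, one-sided α = 0.05, exact p-values, 14 evaluable per arm. From section 12.E: 1:1 allocation and two strata. Assumption: the same response rates in both strata, since the plan states none by stratum.

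**Formula, unstratified.** With X responders of n in Arm 1 and Y of n in Arm 2, the one-sided Fisher p-value is the hypergeometric probability of Y or more responders in Arm 2, given the total X + Y. Power is the sum of b(x; n, p1) × b(y; n, p2) over all outcomes with p ≤ 0.05, where b is the binomial probability.

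At n = 14 the test rejects when Y is at least the value shown:

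| X | 0 | 1 | 2 | 3 | 4 | 5 | 6 | 7 | 8 | 9 | 10 |
|---|---|---|---|---|---|---|---|---|---|---|---|
| Y ≥ | 4 | 6 | 8 | 9 | 10 | 11 | 12 | 13 | 13 | 14 | 14 |

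It never rejects for X ≥ 11.

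**Reproducing Table 12.2 (14 per arm).** Each cell shows printed / Fisher power, in %:

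| Arm 1 | 70% | 75% | 80% | 85% |
|---|---|---|---|---|
| 15% | 85 / 85.1 | 91 / 91.4 | 96 / 95.7 | 98 / 98.2 |
| 20% | 76 / 75.5 | 85 / 84.3 | 91 / 91.1 | 96 / 95.7 |
| 25% | 65 / 64.5 | **80 / 75.2** | 84 / 84.3 | 91 / 91.4 |
| 30% | 53 / 53.0 | 65 / 64.5 | 76 / 75.5 | 85 / 85.1 |

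Outside the design cell, printed minus computed runs from -0.40 to +0.71. In the design cell it is +4.84.

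**Reproducing Table 12.1.** The smallest equal n with Fisher power of 80% or more:

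| Arm 1 | 70% | 75% | 80% | 85% |
|---|---|---|---|---|
| 15% | 12 | 10 | 9 | 9 |
| 20% | 15 | 12 | 10 | 9 |
| 25% | 18 | **15** (printed 14) | 12 | 10 |
| 30% | 23 | 18 | 15 | 12 |

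The other 15 entries match the printed ones exactly.

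**Stratified exact test.** The p-value is the upper tail of the total Arm 2 responders, with each stratum's total fixed (the convolution of two hypergeometrics). Every split with equal arms was enumerated, with the same rates in both strata. Power for 25/75:

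| n per arm | Fisher | Stratified exact |
|---|---|---|
| 12 | 76.6% | - |
| 13 | 71.2% | 70.2% to 74.7% |
| 14 | 75.2% | 75.4% to 76.3% |
| 15 | 80.4% | 80.4% to 80.6% |

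Under this test the design cell of Table 12.2 is 3.7 to 4.6 points too high, and the other 15 cells agree within 1.6 points. Table 12.1 fits it less well: the stratified test gives 13 for 20/75 and 25/80 (printed 12) and 8 for 15/85 (printed 9).

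**Other methods at 14 per arm.** None explains the 80%: one-sided mid-p 86.2%; pooled z, enumerated exactly, 86.5%; normal approximation 87.6% one-sided and 78.6% two-sided; continuity-corrected 76.4% one-sided. The nearest, the two-sided normal at 78.6%, gives 68.3% for 25/70, where 65% is printed.

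**Caption.** At a two-sided 5% level (2.5% in one tail), Fisher gives 63.1% at 14 per arm and needs 18 per arm for 25/75. It matches only one of the 16 printed sizes (15/85), so the entries are one-sided.

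**Unevaluable patients.** Starting from 15 per arm, one loss in each arm leaves 75.2% to 78.7% over all stratum combinations, with the same rates in both strata.

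**Different rates by stratum.** Two equal strata (7 per arm each), averaging 25/75, with the 50-point effect in each:

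| Shift from the mean (points) | 0 | ±5 | ±10 | ±12.5 | ±14 | ±15 | ±20 |
|---|---|---|---|---|---|---|---|
| Power at 14 per arm | 75.4% | 75.8% | 77.4% | 78.9% | 80.0% | 81.0% | 87.1% |

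**The case against.** - **It changes little in practice.** This is a pilot, 15 per arm are already to be randomized, and the analysis p-value does not depend on the planned power. This stands, and it is why the correction concerns the reported figure and not the design.
- **Strata could differ.** If response rates differ enough between strata, 14 per arm does reach 80%. With equal strata that takes a difference of about 28 points (±14). The plan states no such difference, and the other 15 cells fit a calculation without one.
- **The range could be wider.** With a small imbalance between arms within strata, the stratified power at 14 per arm is 76.2% to 77.0%. This stands, but it is still short of 80%.
- **A single loss need not cost 80%.** With 15 vs 14 evaluable, Fisher power is 83.4%, although the stratified test gives 75.2% to 82.5%, depending on where the loss falls. Losing two patients from the same arm (15 vs 13) gives 76.0% under Fisher. So the allowance is not always used up by the first loss, but it does not cover one loss in each arm.
- **Uneven steps are only suggestive.** Exact power moves in a sawtooth, so an irregular row proves nothing alone. This stands; the enumeration is the proof.
- **Table 12.1 does not match its named test.** Its entries follow unstratified Fisher, while the text names a stratified exact test. This stands as a separate mismatch. The design cell is wrong under both.

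**Conclusion.** The concern holds. With 14 evaluable per arm, exact one-sided power for 25% vs 75% is 75.2% (Fisher) or 75.4% to 76.3% (stratified exact, equal arms), not 80% or more. The overstatement is about 4 to 5 points of power, or one patient per arm. It assumes the same response rates in both strata. About 80% is met if all 30 randomized patients are evaluable; it is not preserved after one loss in each arm. The arithmetic is certain. The point must be corrected because the sample-size claim for the primary endpoint rests on this cell.

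**What to change.** - In the 12.F sentence and the 25%/75% cell of Table 12.2, state about 75% power with 14 evaluable per arm. Add that power is about 80% with 15 evaluable per arm, and that both figures assume the same response rates in both strata.
- In Table 12.1, change the 25%/75% entry from 14 to 15.
- As an editorial correction, change the Table 12.1 caption from two-sided to one-sided.

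While editing, it would help to note that the Table 12.1 entries come from the unstratified Fisher test; the corrections above do not depend on this.

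The cost is one sentence, two cells and one caption, and a less favourable power statement. The number randomized, the test, alpha and the analysis stay as they are.

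### At 14 evaluable per arm the primary exact test, read as the conditional test, has a maximum one-sided error of about 2% and about 75% power for 25% vs 75%; an unconditional exact p-value keeps 5% and recovers power

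*Combined protocol and SAP*

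**What the plan says.** - **Level.** Section 12.G.1 sets the primary endpoint apart from all others: "the comparison between arms will be conducted at the one-sided 0.05 significance level".
- **Test.** Section 12.G.3 specifies a CMH comparison stratified by predicted survival (below 18 months, or 18 months and above), and adds "Due to the small sample size, exact p-values will be computed".
- **Sizing.** Section 12.F assumes 25% responders in Arm 1 and 75% in Arm 2, with 14 evaluable per arm, and aims for a sample size "with 80% power at the one-sided 5% significance level". On method it says: "These calculations are based on the stratified Mantel-Haenszel test with exact p-values". Table 12.2 prints 80% for this scenario. The caption of Table 12.1 instead reads "with 80% power at the two-sided 5% significance level", although its entries match a one-sided test.
- **Evaluable numbers.** Section 12.F randomizes 15 per arm to allow for unevaluable patients. Section 12.C.2.6 makes evaluability depend on completing sipuleucel-T and having a month-6 assessment.

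The plan does not give the true size of the test and mentions no unconditional alternative.

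**The concern.** A conditional exact test fixes the number of responders in each stratum and judges the arm split given those totals. With about 28 patients only a few p-values are attainable, and the largest one at or below 0.05 is often far below it. The test then spends only part of the error the plan allows, and power is lost with it. This is the trial's only powered question. At 14 vs 14, a true 25% vs 75% difference would be missed about one time in four, against about one in seven for an exact test that uses more of the permitted 5%.

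**Working it through.** **Inputs.** One-sided 5% (12.G.1); 25% vs 75%, 14 evaluable per arm, target power 80% (12.F); two strata (12.G.3). The documents give no stratum sizes, so the splits below are assumptions.

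**Step 1: why the test is conservative.** Take 14 vs 14 without strata and m responders in all. Given m, the Arm 2 count Y has P(Y = y) = C(14, y)·C(14, m − y) / C(28, m).

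- m = 14: P(Y ≥ 10) = 1,142,975 / 40,116,600 = 0.0285, and P(Y ≥ 9) = 5,150,979 / 40,116,600 = 0.128. The test must stop at 10, spending 2.85%.
- m = 13: P(Y ≥ 10) = 398,776 / 37,442,160 = 0.0107, and P(Y ≥ 9) = 2,402,778 / 37,442,160 = 0.064. It spends 1.07%.

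**Step 2: reproduce the plan.** Let R be all tables with conditional p ≤ 0.05. Power is the sum over R of Bin(x; 14, p1)·Bin(y; 14, p2). The Arm 1 = 25% row of Table 12.2 comes out as follows:

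| Arm 2 rate | 70% | 75% | 80% | 85% |
|---|---|---|---|---|
| Printed | 65% | 80% | 84% | 91% |
| Recomputed | 64.5% | 75.2% | 84.3% | 91.4% |

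The other 12 cells agree within 1 point, so 15 of 16 match. The exception is the design scenario. In Table 12.1, 15 of 16 entries match exactly; the 25%/75% entry should be 15 per arm, not 14.

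**Step 3: true size.** With both arms at a common rate π, sum the same probabilities over R and maximise over π. The result is 2.08% without strata, so 2.08 / 5 = 42% of the permitted error is used. With two strata, the conditional p-value is the upper tail of the sum of two independent hypergeometric counts, and size is maximised over both stratum rates.

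**Step 4: the alternative.** Let p_C be the conditional exact p-value. Define p_U = max over (π1, π2) of P(p_C of a random table ≤ observed p_C), for the observed arm-by-stratum sizes, and reject if p_U ≤ 0.05. Given any responder totals, P(p_C ≤ c) ≤ c. Averaging over totals gives p_U ≤ p_C, so every conditional rejection is kept.

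**Step 5: full enumeration at 25% vs 75%** (size maximised over a grid of null rates; strata written as Arm 1 + Arm 1 / Arm 2 + Arm 2):

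| Evaluable | Strata | Conditional: max size | Conditional: power | Unconditional: max size | Unconditional: power | Gain (points) |
|---|---|---|---|---|---|---|
| 14 vs 14 | none | 2.1% | 75.2% | 4.4% | 86.2% | 11.0 |
| 14 vs 14 | 7+7 / 7+7 | 1.9% | 75.4% | 4.8% | 86.3% | 10.9 |
| 14 vs 14 | 10+4 / 10+4 | 2.2% | 75.6% | 4.4% | 86.2% | 10.6 |
| 14 vs 14 | 9+5 / 8+6 | 2.4% | 76.2% | 4.8% | 86.6% | 10.5 |
| 13 vs 13 | none | 2.4% | 71.2% | 3.8% | 82.1% | 10.8 |
| 13 vs 13 | 7+6 / 7+6 | 2.2% | 70.7% | 4.9% | 82.7% | 12.0 |
| 15 vs 15 | 8+7 / 8+7 | 2.2% | 80.5% | 5.0% | 89.5% | 9.0 |
| 14 vs 13 | 7+7 / 7+6 | 2.7% | 78.7% | 4.9% | 84.5% | 5.8 |
| 15 vs 14 | none | 3.1% | 83.4% | 4.4% | 84.7% | 1.3 |
| 15 vs 14 | 8+7 / 7+7 | 2.8% | 81.6% | 5.0% | 86.7% | 5.1 |
| 15 vs 14 | 10+5 / 10+4 | 2.4% | 78.7% | 4.7% | 85.9% | 7.3 |
| 12 vs 12 | none | 3.2% | 76.6% | 5.0% | 78.8% | 2.2 |
| 12 vs 12 | 6+6 / 6+6 | 2.4% | 70.5% | 4.9% | 79.3% | 8.9 |

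Sizes shown as 5.0% were 0.0495 to 0.0499 before rounding.

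**Step 6: choice of ordering.** Ordering by the CMH Z statistic is also valid, but it did no better than this by any material amount and was often worse with unequal totals: a gain of 2.7 points instead of 5.1 at 15 vs 14 (8+7 / 7+7).

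**The case against.** Nothing here is invalid. A conditional exact test keeps one-sided error at or below 5%, and choosing it over an unconditional test is a recognised preference, defensible in an open-label pilot already tested at one-sided 5%. That stands: this is lost efficiency, not loss of error control.

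A reader might infer that 2% size and an 11-point gain are general properties of this trial. The documents do not support that. They randomize 15 per arm and expect some to be unevaluable, so 14 vs 14 is one possible outcome among several. At 15 vs 14 the conditional test can already reach 83% power at a size of 3.1%, and the gain can shrink to about 1 point. Nor does the shortfall against 80% hold at every evaluable number; at 15 vs 15 the conditional test reaches about 80%.

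It is also fair that the plan never uses the word conditional. The reading rests on the match with the sizing tables. Section 12.G.3 names Zelen's test, which examines whether odds ratios are equal across strata, not whether the arms differ. That wording needs correcting in its own right, but correcting it to the conditional exact CMH test would leave the conservatism in place.

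The preference argument weakens once tables are ordered by the conditional p-value: the new test rejects whenever the old one does and still respects 5%. What is given up is familiarity and off-the-shelf code.

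**Conclusion.** The point holds as a cheap improvement, on the reading that the exact p-values are conditional. At 14 vs 14 evaluable, maximum size is about 2% and power for 25% vs 75% is about 75%, under the stated 80%. In the 12-to-15-per-arm layouts examined, maximum size is about 2 to 3% and power about 70 to 83%.

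The unconditional version gains 10 to 11 points at 14 vs 14, 11 to 12 at 13 vs 13, about 9 at 15 vs 15 and about 6 at 14 vs 13. At 15 vs 14 the gain is 1 to 7 points, and at 12 vs 12 it is 2 (no strata) to 9 (6+6), depending on the assumed split. The 14 vs 14 gain is measured from the recomputed 75%; against the printed 80%, which does not reproduce, it is 86 − 80 = about 6 points. All gains are for 25% vs 75% and will differ at other response rates.

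**What to change.** In 12.G.3, replace the exact p-value with an unconditional exact one:

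1. Order tables by the one-sided conditional exact stratified (CMH) p-value (a Boschloo-type test).
2. For the observed arm-by-stratum sizes, compute the tail probability and maximise it over the common response rate in each stratum, on a fine grid.
3. Declare success if the result is at most 0.05.

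Fix the ordering and the program before any outcome data are seen. Remove the reference to Zelen's test from the arm comparison. Recompute Tables 12.1 and 12.2 on the new test, with captions stating one-sided. Report the conditional exact p-value as a sensitivity analysis.

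The cost is a protocol amendment, which 12.G.1 already requires for changes to primary methods, a short custom program (8 × 8 × 8 × 8 = 4,096 tables for two strata of 7 vs 7), and a p-value that readers will know less well. No extra patients are needed.
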